# 7.4. Analysis of the Secondary Efficacy Parameter

#### 7.4.1. Duration of FEV1 Response

Duration of FEV1 response is defined as the interval between the onset of response and the earliest of BOS progression, loss of clinical benefit as determined by the investigator, or death, in which:

• The time of onset of response is defined as the earliest assessment date when ≥ 10% absolute increase in FEV1 compared with pretreatment baseline (confirmed by 2 consecutive spirometric assessments ≥ 1 week apart) is achieved.

- BOS progression is defined as ≥ 10% absolute decrease in FEV1 compared with
  pretreatment baseline observed in at least 2 consecutive spirometric assessments at least
  3 weeks apart. The onset of BOS progression is the earliest date of such qualified
  assessments.
- Time of loss of clinical benefit is the date when a participant discontinues treatment due to "lack of efficacy."

Participants with no observed BOS progression, loss of clinical benefit, or death at the time of database lock or discontinuation will be censored at the time of last valid FEV1 assessment.

Duration of FEV1 response will be assessed using the Kaplan-Meier method for participants who achieve a response. Median duration and 95% CIs will be estimated.

### 7.4.2. Time to Progression or Death

Time to progression or death, defined as the interval between the start of itacitinib treatment and BOS progression (defined as a  $\geq$  10% absolute decrease in FEV1 from pretreatment baseline observed in at least 2 consecutive spirometric assessments at least 3 weeks apart) or death. The time of BOS progression follows the same definition as in Section 7.4.1. Participants with no observed BOS progression or death at the time of database lock or discontinuation will be censored at the time of last valid FEV1 assessment.

Time to progression or death will be estimated by the Kaplan-Meier method. Median duration and 95% CIs will be estimated.

#### 7.4.3. SGRQ Total Score

The SGRQ (Jones et al 1991) is a disease-specific instrument designed to measure impact on overall health, daily life, and perceived well-being in patients with obstructive airway disease. It consists of 50 items covering 3 domains: symptoms (8 items), activity (16 items), and impacts (26 items).

A component score will be calculated for each of the 3 domains. If more than 2 items in the symptoms domain are missing, the symptom component score will set to be missing. If more than 4 items in the activity domain are missing, the activity component score will set to be missing. If more than 6 items in the impacts domain are missing, the impacts component score will set to be missing.

One total score will be calculated if none of the component scores is missing. All scales have a score range between 0 and 100 with higher scores indicating a worse quality of life.

Summary statistics will be provided for change from baseline in SGRQ component scores and the total score at each scheduled visit.

#### 7.4.4. QOL-SF-12 Questionnaire

The QOL-SF-12 v2 (Ware et al 1996) is a 12-item subset of the QOL-SF-36 v2 scale that captures changes in health status during the course of treatment. The QOL-SF-12 assesses 8 health concepts related to limitations in physical activities, social activities, bodily pain, general mental and physical health, and vitality.

For this questionnaire, 1 component score will be provided for each of 8 health concepts. Two summary scores, physical component summary and mental component summary, will also be provided. For each item, a higher score indicates a better health state.

Summary statistics will be provided for change from baseline in 2 scales at each scheduled visit.

#### 7.4.5. EQ-5D-3L

The EQ-5D-3L (EuroQol Research Foundation 2017) essentially consists of 2 components: the EQ-5D descriptive scale and the EQ-VAS.

The EQ-5D-3L descriptive system comprises the following 5 dimensions, each describing a different aspect of health: mobility, self-care, usual activities, anxiety/depression, and pain/discomfort. Each dimension has 3 levels: no problems, some problems, and extreme problems. The EQ-VAS records the respondent's self-rated health on a vertical visual analog scale on which the endpoints are labeled as "the best health you can imagine" and "the worst health you can imagine."

At each specific visit (starting on Day 1), the participant will be asked to indicate their health state. Missing values will not be imputed. The categorical outcomes for the 5 dimensions (mobility, self-care, usual activities, anxiety/depression, and pain/discomfort) will be summarized by visit, and summary statistics will include frequency and percentage. The change from baseline in EQ-VAS score will be summarized.

#### 8. PHARMACOKINETICS AND PHARMACODYNAMICS

### 8.1. Pharmacokinetic Analyses

#### 8.1.1. Pharmacokinetic Data

Participants will arrive at the clinic having withheld their morning dose of itacitinib. Pharmacokinetic samples will be obtained at the visits indicated in Protocol Table 3. After the predose PK sample is drawn, participants will take the dose of itacitinib. Predose is defined as within 24 hours before administration of itacitinib. The exact date and time of the PK blood draws will be recorded on the eCRF along with the date and time of the last dose of study drug and details of the last meal before the blood draw. Instructions for sample preparation and shipping will be provided in the Laboratory Manual. Sample collection times and windows for itacitinib are shown in Table 2. Adjustments to the timing of blood sampling postdose may be made based on emerging PK data; however, no more than 6 postdose timepoints will be used, and the maximum scheduled timepoint will be no greater than 12 hours postdose.

**Table 2:** Sample Collection Times for Pharmacokinetic Assessments of Itacitinib

Visit	Timing of Sample Relative to Itacitinib Administration			
Baseline (Day 1) a	Predose	$1 \text{ h} \pm 15 \text{ min}$	$2 h \pm 30 min$	5 h ± 60 min
Week 4	Predose (-30 min)	1 h ± 15 min	2 h ± 30 min	5 h ± 60 min

[figure not shown]
<sup>a Phase 1 participants only.

# 8.1.2. Participant Demographic, Clinical Laboratory, Disease-Related, and Pharmacogenomic Variables and Concomitant Medications

Participant demographic assessments (eg, age, weight, BMI, sex, race) and clinical laboratory measurements (eg, FEV1, creatinine clearance, serum albumin, total bilirubin, alkaline phosphatase, alanine aminotransferase, aspartate aminotransferase) may be explored as time-independent predictors of PK variability. Concomitant medications may be explored as time-dependent covariates in the population PK analysis.

#### 8.1.3. Pharmacokinetic Analyses

The noncompartmental analysis for itacitinib PK will be performed using WinNonlin® v8.0 or later (Certara, Princeton, NJ). The following PK parameters will be estimated where possible: $C_{max}$ , $t_{max}$ , $C_{min}$ , $AUC_{0-t}$ , $AUC_{0-\tau}$ , $t_{1/2}$ , $Cl/F$ , and $V_z/F$ .	

### **8.1.4.** Report

A PK report will be prepared to include listings of observed itacitinib plasma concentration data and estimated PK parameters in accordance with guidance of both US and EU regulatory authorities.

### 8.2. Pharmacodynamic Analyses

Baseline and pharmacodynamic analyses of serum cytokines, will be conducted as follows:

- Baseline differences in inflammatory mediators between responders and nonresponders will be assessed using:
  - Unadjusted logistic regression models, with FEV1 response as a binary variable.
  - Unadjusted general linear models, with change in FEV1 as a continuous variable.
  - Statistically significant unadjusted models will be adjusted for baseline FEV1, age, sex, itacitinib dose, and prior immunosuppressive therapy. If fewer than 10 observations are available per covariate, covariates will be removed in order from weakest to strongest statistical association with the inflammatory mediator (outcome) of interest, until at least 10 observations per covariate are available. Alternatively, if variables are determined to be biologically relevant to the analysis, the model will include the principal component analysis scores for the covariates. Only scores with eigenvalues > 1 will be included.
- Pharmacodynamic changes from baseline will be compared between responders and nonresponders using paired t-tests.
- Significance will be reported at p < 0.05 and fold change > |15%|.

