2.3. Benefit/Risk Assessment

The potential benefit for itacitinib in post-lung transplant BOS patients is derived from the biologic similarity to cGVHD, with each entity sharing common features such as increased proinflammatory cytokines, presence of CD4, CD8, and Th17 cell infiltrate, as well as subsequent recruitment of B cell, NK cell, and APCs. Preclinical models and small clinical studies have demonstrated significant activity when JAK inhibitors are used in cGVHD, including improvement and stabilization in FEV₁ in patients with lung cGVHD, suggesting that JAK inhibitors may also have potential utility in treating post-lung transplant BOS.

Risks to study participants may be minimized by compliance with the eligibility criteria and study procedures as well as close clinical monitoring and adherence to dose modification guidelines for toxicity. Additionally, the safety profile of the 3 doses to be evaluated has been established in prior studies. Risks related to myelosuppression and bleeding should be further managed in accordance to standard institutional practices for administration of hematopoietic growth factors and transfusion support. Risks related to infections should be managed through continued prophylaxis and prompt identification and treatment.

In September 2021, analysis of the data from the Phase 1 portion of the study revealed evidence of clinical benefit in a subset of participants with a manageable safety profile. The sponsor decided not to proceed to Phase 2 of the study for reasons unrelated to the benefit/risk of itacitinib in the study population. The sponsor will continue to consider the benefit/risk favorable for participants who are continuing on itacitinib as of Protocol Amendment 5.

There may be unforeseen and potentially serious risks with itacitinib. More detailed information about the known and expected benefits and risks and reasonably expected AEs of itacitinib may be found in the [IB](#).

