# 3.2. Control of Type I Error

No formal efficacy hypotheses will be tested, and no alpha control will be implemented.

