### 7.1. General Considerations

All efficacy analyses will be done by treatment group using the FAS. The SGRQ Total Score, QOL-SF-12 Questionnaire, and EQ-5D-3L analyses will not be performed due to the early study termination.

For continuous measurements, summary statistics will include sample size, mean, median, standard deviation, standard error of the mean, minimum, and maximum. For all continuous variables, both the actual value and change and/or percentage from baseline (if available) will be analyzed. For categorical measurements, summary statistics will include sample size, frequency, and percentages.

All by-visit analyses will include the EOT and follow-up visits if the data are available.

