### 7.3. Analysis of the Primary Efficacy Parameter

In Phase 1, the primary endpoint is FEV1. Change and percentage change from baseline in FEV1 and FEV1 % predicted will be summarized by visit and treatment group.

In Phase 2, the primary endpoint is  $FEV_1$  response rate through the Week 12 visit, defined as the proportion of participants demonstrating a  $\geq 10\%$  absolute increase in  $FEV_1$  compared with baseline, confirmed by 2 consecutive spirometric assessments  $\geq 1$  week apart. The primary analysis will be conducted once the last participant completes the Week 12 visit or withdraws from the study. If a participant withdraws from the study before Week 12, or there is no  $FEV_1$  data up to and including Week 12, the participant will be considered as a nonresponder. Summary statistics and 95% CIs will be provided. Confidence intervals will be calculated based on the exact method for binomial distributions.

In Phase 1,  $FEV_1$  response rate will also be calculated due to the fact that duration of  $FEV_1$  response is a secondary efficacy endpoint in Phase 1.

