## 11.2. Changes to the Statistical Analysis Plan

#### **11.2.1. Amendment 1**

The following updates were made for SAP Amendment 1 to align with early study termination:

- The planned tables, figures, and listings were updated in Appendix A to remove those that were not needed.
- Analyses for SGRQ Total Score, QOL-SF-12 Questionnaire, and EQ-5D-3L were removed.
- Text was updated to address the analyses not being performed.

Other minor administrative changes have been incorporated throughout and are noted in the redline version of the document.

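### SAP 8.2 names paired t-tests to compare pharmacodynamic change between responders and nonresponders, who are different, unmatched participants

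*SAP*

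**What the plan says.** SAP 8.2 (Pharmacodynamic Analyses) sets out two kinds of cytokine analysis.

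- **Baseline mediators.** The section opens this part with "Baseline differences in inflammatory mediators between responders and nonresponders will be assessed using" and then lists unadjusted logistic regression on FEV1 response, unadjusted general linear models on FEV1 change, and covariate-adjusted versions of those that reach significance.
- **Change from baseline.** The whole instruction is "Pharmacodynamic changes from baseline will be compared between responders and nonresponders using paired t-tests".

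The reporting criterion for the section is p below 0.05 together with an absolute fold change above 15%.

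Response is a yes/no result for each participant. SAP 7.3 defines it as a confirmed absolute FEV1 increase of at least 10%. For a participant who withdraws before Week 12 or has no FEV1 data through Week 12, it says "the participant will be considered as a nonresponder". SAP 3.1 randomizes Phase 1 participants 1:1:1 to dose level and describes no other allocation or pairing.

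The SAP is dated 12 APR 2023 and was amended on 26 AUG 2024 because of early termination. Section 11.2.1 says of that amendment: "Text was updated to address the analyses not being performed". Section 7.1 then names what was dropped from efficacy: "The SGRQ Total Score, QOL-SF-12 Questionnaire, and EQ-5D-3L analyses will not be performed due to the early study termination". Section 8.2 carries no such statement.

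**The concern.** The test and the contrast do not fit together. The contrast is between two sets of people, and the test works only on matched pairs. This is also the only analysis in 8.2 that relates cytokine change to FEV1 response, because the regression models concern baseline mediators. The one question about on-treatment pharmacodynamics and response therefore has no workable method.

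The practical risk lies in what an analyst does instead. The nearest procedure that keeps the word paired is a baseline-versus-on-treatment test run separately in responders and in nonresponders. If one result is significant and the other is not, it is tempting to report that the mediator moved differently in the two groups. That inference is invalid. A significant and a nonsignificant result can easily come from the same true change, especially when one group is much smaller.

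**Working it through.** The SAP gives no sample size, power or effect size for this comparison, so there is no planned figure to reproduce. The check has two parts.

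**1. Can the named test be run?**

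- A paired t-test takes one difference per pair, with degrees of freedom equal to the number of pairs minus 1.
- Each participant has one response status, so the groups do not overlap. Nothing in either document links a given responder to a given nonresponder.
- The within-participant pairing (on-treatment against baseline) has already been used to form the change score. It is not available a second time.
- With unequal groups, for example 5 and 19, a paired routine fails because the arrays differ in length. With 12 and 12 it would run, but only on an arbitrary pairing.
- A two-sample test on the changes has n1 + n2 − 2 = 24 − 2 = 22 degrees of freedom in its pooled form, if all 24 participants have data.

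**2. What if it is run as a paired test within each group?** The SAP does not specify this fallback, so the figures are hypothetical.

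Inputs:

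- 24 participants (SAP 3.3), all assumed evaluable.
- Splits of 5 vs 19, 8 vs 16 and 12 vs 12. The first applies the 20% Phase 2 planning rate in SAP 3.3: 0.20 × 24 = 4.8, about 5. The other two show a range.
- Assumed: normal change scores, two-sided 0.05 (the SAP does not state sidedness), and the same true change of d SD in both groups.

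Formulas: for a group of size n, the power p of the paired test comes from the noncentral t distribution with n − 1 degrees of freedom and noncentrality d√n. The chance that exactly one group is significant is p1(1 − p2) + p2(1 − p1).

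Worked examples:

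- d = 0, any split: 2 × 0.05 × 0.95 = 0.095.
- d = 0.8, 5 vs 19: p1 = 0.281 and p2 = 0.909, so 0.281 × 0.091 + 0.909 × 0.719 = 0.026 + 0.654 = 0.68.

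| True change in both groups (SD) | 5 vs 19 | 8 vs 16 | 12 vs 12 |
|---|---|---|---|
| 0 | 0.095 | 0.095 | 0.095 |
| 0.2 | 0.179 | 0.177 | 0.176 |
| 0.4 | 0.405 | 0.381 | 0.370 |
| 0.6 | 0.625 | 0.542 | 0.499 |
| 0.8 | 0.679 | 0.503 | 0.409 |
| 1.0 | 0.596 | 0.333 | 0.207 |
| 1.2 | 0.470 | 0.176 | 0.067 |

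On a 0.01 SD grid the peaks are 0.683 at 0.76 SD (5 vs 19), 0.553 at 0.66 SD (8 vs 16) and 0.500 at 0.62 SD (12 vs 12). Every entry is a trial in which the groups truly do not differ.

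**Corrected test.** Welch t-test on the change scores, 200,000 simulated trials per setting, equal SDs:

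| True group difference (SD) | 5 vs 19 | 8 vs 16 | 12 vs 12 |
|---|---|---|---|
| 0 (false positives) | 0.057 | 0.051 | 0.049 |
| 0.5 (power) | 0.146 | 0.191 | 0.212 |
| 1.0 (power) | 0.405 | 0.576 | 0.645 |

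**The case against.** The strongest reply is that this is a drafting slip with little consequence. The sentence already states a between-group contrast, the baseline part of the same section uses between-participant models, and a programmer facing unequal groups would probably use an unpaired test. On efficacy, SAP 3.2 says "No formal efficacy hypotheses will be tested, and no alpha control will be implemented", and no FEV1, time-to-event or safety result depends on this comparison. That is fair and limits the importance of the point. It does not make the instruction correct, and a plan should not rely on the programmer to replace the test it names.

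A second reply is that the analysis may no longer be planned. Appendix A lists no pharmacodynamic display, and Protocol Amendment 5 includes the pharmacodynamic section among those with assessments updated or removed. Other analyses still described in the SAP, such as laboratory shift tables and clinically notable event summaries, also have no table in Appendix A and no disclaimer. Whether the analysis survives is therefore uncertain. Absence from Appendix A does not settle it, since pharmacokinetics has no display there either and goes to a separate report. What can be said is that 8.2 still instructs the analysis.

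Three smaller points stand:

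- The nonresponder rule in SAP 7.3 sits in the Phase 2 paragraph, and Phase 2 did not proceed. The Phase 1 groups are disjoint by logic, not because that sentence covers them.
- The illustrated range depends on the grid. At 12 vs 12 disagreement falls to 0.6% at 1.5 SD, and at 2 vs 22 it is about 88% at 0.8 SD.
- Welch is one of several valid choices. A rank-based test or a linear model would also make the comparison.

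**Conclusion.** The concern holds. The test named in SAP 8.2 cannot compare responders with nonresponders. This follows from the structure of the data and depends on none of the numerical assumptions.

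The size of the harm is conditional. If the fallback of two within-group tests were used and read as a group comparison, a false impression of difference would arise in about 7% to 68% of trials over the splits and effect sizes shown, against about 5% for a Welch test. Those figures rest on normal changes, 24 evaluable participants, the assumed splits and the assumed fallback. The Welch figures also assume equal SDs.

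The effect on the trial's conclusions is limited. The wording does not itself create a choice made after seeing data. Protocol 2.3 records that "In September 2021, analysis of the data from the Phase 1 portion of the study revealed evidence of clinical benefit", so the SAP of 2023 and its 2024 amendment already postdate that analysis. It should be fixed because an instruction in the current SAP cannot be carried out as written.

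**What to change.** Replace the sentence in SAP 8.2 with:

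> Change from baseline in each mediator will be compared between responders and nonresponders using a two-sample (Welch) t-test; paired t-tests will be used only to describe change from baseline within a group.

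Since the reporting criterion is a fold change, the same edit could usefully state the scale of the change (absolute or log-ratio) and the visit.

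If the analysis was dropped at early termination, say so in 8.2 instead, as 7.1 does for the quality-of-life analyses.

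The cost is one sentence and a different procedure call, with no new data. Any report should note the low power of the corrected test: at 5 vs 19, about 15% for a 0.5 SD group difference and 40% for 1.0 SD. A nonsignificant result would say little.

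### SAP 8.2 calls exploratory cytokine associations significant at a nominal threshold over three tests per mediator, with no multiplicity control, and adjusts only the models that already passed

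*SAP*

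**What the plan says.** SAP 8.2 (Pharmacodynamic Analyses) opens with "Baseline and pharmacodynamic analyses of serum cytokines, will be conducted as follows". Each cytokine then enters three analyses:

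- baseline level against binary FEV1 response: "Unadjusted logistic regression models";
- baseline level against continuous change in FEV1: "Unadjusted general linear models";
- change in the cytokine: "Pharmacodynamic changes from baseline will be compared between responders and nonresponders using paired t-tests".

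The reporting rule is "Significance will be reported at p < 0.05 and fold change > |15", where the 15 is a percentage.

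On adjustment: "Statistically significant unadjusted models will be adjusted for baseline" FEV1, age, sex, dose and prior immunosuppression. Covariates are dropped, weakest association first, until there are at least 10 observations for each one kept. A second route follows: "Alternatively, if variables are determined to be biologically relevant to the analysis, the model will include the principal component analysis scores", limited to components with eigenvalues above 1.

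The only general statement on error control is in SAP 3.2: "No formal efficacy hypotheses will be tested, and no alpha control will be implemented".

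**The concern.** SAP 3.2 waives alpha control in the setting of efficacy hypotheses, and SAP 7.2 marks those as not applicable. SAP 8.2 nevertheless computes p-values and labels results significant, and it is the only place in the SAP with a p-value threshold. A reader of the report would see the label without knowing how many tests lay behind it.

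The adjustment rule is a separate problem. It adds no unadjusted false positives. But adjusted estimates will exist only for mediators whose unadjusted association happened to be large, and an association masked by confounding is never examined. Nothing says whether a finding must survive adjustment to be reported, or who decides that the principal-component route applies.

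At stake is how far any reported cytokine association in about 24 participants can be read. The efficacy and safety summaries are not affected.

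**Working it through.** **Inputs.** Per-test threshold 0.05 (SAP 8.2; two-sided assumed). Three test types per mediator (SAP 8.2). About 24 participants (SAP 3.3), with no Phase 2 data because the sponsor did not proceed (Protocol 2.3). Assumed response rate 20% (SAP 3.3), so 24 × 0.20 = 4.8, or about 5 responders. The number of mediators, m, is not in the available text; 5, 10 and 20 are assumptions. SAP 8.2 states no error rate, so there is no plan figure to reproduce.

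**Step 1: independent tests, nothing real.** Chance of at least one p < 0.05 in k tests = 1 − 0.95^k; expected number = 0.05k.

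| m | one test each (k = m) | expected | three tests each (k = 3m) | expected |
|---|---|---|---|---|
| 5 | 22.6% | 0.25 | 53.7% | 0.75 |
| 10 | 40.1% | 0.5 | 78.5% | 1.5 |
| 20 | 64.2% | 1.0 | 95.4% | 3.0 |

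The chance passes 50% at 14 mediators with one test each (1 − 0.95^14 = 51.2%) and at 5 mediators with three tests each.

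**Step 2: dependence and the fold-change filter.** The three tests share data, and cytokines are correlated. A null simulation used n = 24; 3, 5 or 8 responders; log-scale SD 0.3, 0.5 or 0.8; correlation between cytokines 0 or 0.5; and 1000 runs per setting. It used Wald logistic, linear and two-sample t-tests, the last in place of the paired test. Adjusted models were not simulated. Chance of at least one finding over all three test types:

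| m | all settings, with filter | 5 responders, SD 0.5, correlation 0: with filter (without) | same, correlation 0.5: with filter (without) |
|---|---|---|---|
| 5 | 31-46% | 39.7% (41.1%) | 37.6% (38.3%) |
| 10 | 47-71% | 67.5% (69.8%) | 54.4% (55.7%) |
| 20 | 66-91% | 89.9% (91.6%) | 72.1% (73.5%) |

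For a single cytokine the figure is about 10%. Across settings the filter lowers the chance by at most about 6 percentage points, and in the change comparison it removed none of the p < 0.05 results. At this sample size a difference that reaches p < 0.05 usually exceeds 15% anyway. The simulated figures fall below Step 1 partly because of dependence and partly because the Wald logistic test is conservative with few responders (0.5-3% per test). Likelihood-ratio tests ran at 6-8% per test and would raise them.

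**Step 3: the adjustment rule.** Ten observations per covariate with 24 participants gives 24 / 10 = 2.4, so at most 2 of the 5 listed covariates. Keeping all five needs 5 × 10 = 50 participants. Pruning by observed association will therefore be routine, and the covariates kept may differ from one mediator to the next.

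**Step 4: the third test.** Responders and nonresponders are different people, and the SAP defines no pairing between them. A paired t-test can compare change within a group with zero; it cannot compare the two groups.

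**The case against.** The strongest reply is that this is openly exploratory work. SAP 3.2 says there is no alpha control, SAP Appendix A lists no pharmacodynamic table or listing, Phase 2 did not open, and no document ties a decision to these p-values. That stands as to consequence. It does not justify an unqualified label of significance. Pharmacodynamics is part of the Phase 1 primary endpoint (SAP Table 1) and was a stated basis for choosing the Phase 2 dose (SAP 3). SAP Amendment 1 dropped the quality-of-life analyses but kept 8.2.

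The panel size may also be given elsewhere. Text may be redacted, and the SAP rests on Protocol Amendment 3, whereas Amendment 5 updated or removed the pharmacodynamic assessment section. So one cannot say that the panel is unlimited, only that its size is not in the text at hand. A reader might infer that a chance finding is likely whatever the panel. For 1 to 3 cytokines that is not supported.

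A reader might also infer that any responder signature reported would probably be noise. That does not follow. The figures above are the chance of at least one false positive if nothing is real. The probability that a given finding is false also depends on power and on the share of true associations, and the documents give neither.

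Finally, the adjustment is not without rules: there is an order of removal, a limit per covariate and an eigenvalue cut-off. What lacks definition is the switch between the two routes.

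**Conclusion.** The concern holds as a reporting and selection problem in an exploratory analysis. SAP 8.2 as written would yield findings called significant without control over the number of tests, and adjusted estimates only for mediators already selected by their unadjusted result. The chance of at least one false finding is about 31-46% for 5 mediators, 47-71% for 10 and 66-91% for 20 with all three tests. It becomes more likely than not from roughly 5 mediators if tests are independent and around 10 under the simulated dependence, where the lowest setting is still just under one half. These figures rest on assumed panel sizes, n = 24, 3 to 8 responders, no true association, and a two-sample test in place of the paired one. The 15% filter gives little protection. The point is worth correcting; it does not bear on the trial's efficacy or safety conclusions.

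**What to change.** In SAP 8.2:

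1. State the number of mediators and the number of tests, or point to where they are given.
2. Report effect sizes with 95% CIs for every mediator.
3. Report Benjamini-Hochberg adjusted p-values within each of the three test families, at a false discovery rate fixed in advance (for example 10%). Reserve the word significant for those, and label unadjusted p-values nominal and exploratory.
4. Replace the paired t-test with a two-sample comparison of change before treating it as a family.
5. Fit one prespecified adjusted model for every mediator, with at most 2 covariates under the SAP's own rule. Drop both the unadjusted screen and the principal-component alternative. Choose the covariates on clinical grounds without reference to cytokine results, and record that the choice was made after the Phase 1 data had been analysed (Protocol 2.3).

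The cost is SAP wording and a few lines of code. The downside is that fewer mediators will be called significant. With about 5 responders, even two covariates may be too many for a stable logistic model, so those adjusted results should be read with care.
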